| 2.1 Background | Added: In April 2023, we elected to expand inclusion criteria to include intubated patients with pneumonia (unilateral or bilateral pulmonary infiltrates consistent with lung infection), given reported similar outcomes in critically ill patients with unilateral and bilateral infiltrates (LUNG SAFE study). | This change was made to support the rationale for adding intubated patients with pneumonia to the study population. |
| 2.2.1 Introduction | Added: Pneumonia represents a lung infection with unilateral or bilateral infiltrates, and intubated patients with pneumonia not formally meeting ARDS criteria have been reported to have similar | This change was made to support the rationale for adding intubated patients with pneumonia to the study population. |

NIH-FDA Phase 2 and 3 IND/IDE Clinical Trial Protocol Template

| | | |
|---|--|---|
| | 
outcomes with unilateral or bilateral infiltrates. Pneumonia in intubated patients represents an important spectrum of illness in ARDS, and in fact the most recent NIH lung injury consortium to improve phenotyping in critical illness will enroll subjects with pneumonia, sepsis and ARDS. Furthermore, our preliminary data demonstrating efficacy and safety of inhaled CO in pneumonia baboons is presented below.
 | |
| 3.0 Objectives, 4.1 Overall Study Design, 4.2 Scientific Rationale | 
Objectives were updated to include pneumonia and/or sepsis in the study population.
 | 
Change made to update the study population.
 |
| 5.1 Inclusion Criteria | 
The following changes were made to this section. All patients (age 18 and older) will be eligible for inclusion if they meet all of the following consensus criteria for sepsis and ARDS3, or if they meet the criteria for pneumonia.
 
The following inclusion criteria was added:
 
 • Pneumonia (without ARDS or sepsis) will be defined as a unilateral or bilateral lung infiltrate on chest X-ray or chest CT (not fully explained by effusions, lobar/lung collapse or nodules) in the setting of receiving mechanical ventilation, a new suspected respiratory infection, an increase in SOFA score less than 2 at the time of randomization (baseline). Pneumonia with bilateral opacities, $\text{PaO}_2/\text{FiO}_2$ ratio ≤ 300, or an increase in SOFA score greater than or equal to 2 over baseline will continue to be considered ARDS and sepsis. • Pneumonia (with sepsis, without ARDS) will be defined as a unilateral or bilateral lung infiltrate on chest X-ray or chest CT (not fully explained by effusions, lobar/lung collapse or nodules) in the setting of receiving mechanical ventilation and a new suspected respiratory infection with an increase in SOFA score of ≥ 2 over baseline at the time of randomization. Pneumonia with bilateral opacities, $\text{PaO}_2/\text{FiO}_2$ ratio ≤ 300, or an increase in SOFA score greater than or equal to 2 over baseline will continue to be considered ARDS and sepsis. | 
Inclusion criteria revised to include intubated patients with pneumonia.
 |

NIH-FDA Phase 2 and 3 IND/IDE Clinical Trial Protocol Template

| | | |
|--|--|---|
| 5.4 Strategies for Recruitment and Retention | 
The following language was added to this section:
 
We have expanded inclusion criteria to include subjects with unilateral or bilateral infiltrates intubated for suspected lung infection (pneumonia), given similar outcomes from unilateral or bilateral lung infiltrates in critically ill patients, consistency with our preclinical baboon model of ALI due to pneumococcal pneumonia that had improved outcomes with inhaled CO, and the need to expand enrollment for this study.
 | 
This phase 1b protocol will also include subjects with unilateral or bilateral infiltrates intubated for suspected lung infection (pneumonia). This was added given similar outcomes from unilateral or bilateral lung infiltrates in critically ill patients and for consistency with our preclinical baboon model of ALI due to pneumococcal pneumonia that had improved outcomes with inhaled CO. This may also help with enrollment in this study.
 |
| 9.1 Statistical Hypothesis | 
The following changes were made to this section.
 
Hypothesis: We hypothesize that low dose iCO will be safe and well-tolerated and that the CFK equation-based iCO personalized dosing algorithm will be accurate in achieving a target COHb level of 6-8% in patients with pneumonia (without ARDS and sepsis criteria, and with sepsis but without ARDS criteria) and sepsis-induced ARDS at study entry.
 
We further hypothesize that precision-based iCO therapy will reduce the severity of pneumonia and ARDS and organ failure by suppressing mitochondrial dysfunction, inhibiting inflammasome activation and necroptosis, and accelerating resolution of inflammation.
 | 
This change was made to incorporate the additional strata into the statistical plan.
 |
| 9.4.2 Analysis of the Primary Efficacy Endpoint(s), 9.4.5 Safety Analysis | 
The following language was added: ANOVA will be repeated to assess the effects of treatment, time (over 3 days), entry criteria (ARDS/Sepsis vs. Non-ARDS/Sepsis Pneumonia vs. Non-ARDS/non-Sepsis Pneumonia), and two-way/three-way interactions of time, treatment and entry criteria.
 | 
This change was made to incorporate the additional strata into the statistical plan.
 |

1 PROTOCOL SUMMARY

1.1 SYNOPSIS

Title: A Phase Ib Trial of Inhaled Carbon Monoxide for the Treatment of Pneumonia and Sepsis-induced Acute Respiratory Distress Syndrome (ARDS)

Study Description: Multi-center, prospective, randomized, partially double-blind, placebo-controlled Phase Ib safety clinical trial of inhaled CO (iCO) for the treatment of pneumonia and sepsis-induced ARDS.

Hypothesis: We hypothesize that low dose iCO will be safe and well-tolerated and that the Coburn-Forster-Kane (CFK) equation-based iCO personalized dosing algorithm will be accurate in achieving a target carboxyhemoglobin (COHb) level of 6-8% in intubated patients with pneumonia and sepsis-induced ARDS.

Objectives: **Primary Objective:** To evaluate the safety and accuracy of a CFK equation-based personalized iCO dosing algorithm in intubated patients with pneumonia and sepsis-induced ARDS.

Secondary Objectives: To examine the effects of low dose iCO therapy on biologic readouts in intubated patients with pneumonia and sepsis-induced ARDS.

Endpoints: **Primary Endpoints:** The primary endpoints are:

1. **Safety of iCO**, defined by the incidence of pre-specified administration-related adverse events (AEs) and serious adverse events (SAEs). Administration-related SAEs are: 1) myocardial infarction; 2) stroke; 3) new onset arrhythmia requiring DC cardioversion; 4) worsening hypoxemia^{1,2}; 5) COHb $\geq 10\%$; and 6) increase in lactate by ≥ 2 mmol/L.

2. **Accuracy** of the CFK equation-based personalized iCO dosing algorithm to achieve a COHb level of 6-8%.

Secondary Endpoints:

1. Lung Injury Score (LIS) on days 1-5 and day 7
2. PaO₂/FiO₂ on days 1-5 and day 7
3. Oxygenation index (OI) on days 1-5 and day 7
4. Dead space fraction (Vd/Vt) on days 1-3 and day 7
5. Sequential Organ Failure Assessment (SOFA) scores on days 1-5, 7, 14, and 28
6. Ventilator-free days at day 28
7. ICU-free days at day 28
8. Hospital-free days to day 60
9. Hospital mortality to days 28 and 60
10. Neurocognitive function at 3 and 6 months

[figure not shown]
Exploratory Endpoints:

1. Blood and urine biomarkers of mitochondrial dysfunction (mtDNA), inflammasome activation (IL-18) and necroptosis (RIPK3)

2. Lipid mediators (LM) and specialized pro-resolving mediators (SPMs)

| | |
|--|---|
| Study Population: | This study will enroll 36 adult subjects. All intubated patients \geq 18 years old who meet criteria for pneumonia and/or sepsis and ARDS according to consensus criteria ^{3,4} will be potentially eligible for inclusion. Subjects will be recruited from the medical, surgical, and cardiac intensive care units (ICUs) at each center. |
| Phase: | Phase Ib |
| Description of Sites/Facilities Enrolling Participants: | The trial will be conducted at 6 tertiary care medical centers including Weill Cornell Medicine/New York-Presbyterian Hospital, Brigham and Women's Hospital (BWH), Massachusetts General Hospital (MGH), Duke (Duke University Hospital/ Durham Regional Hospital), Washington University, and New York-Presbyterian Brooklyn Methodist Hospital. |
| Description of Study Intervention: | Participants will receive algorithm-specified iCO dose (not to exceed 500 ppm) or medical grade air, to achieve COHb of 6-8% over 90 minutes for three consecutive days. |
| Study Duration: | Enrollment will take place over 27 months followed by 9 months for data analysis and dissemination of study results. |
| Participant Duration: | 6 months |

1.2 SCHEMA

1.3 SCHEDULE OF ACTIVITIES (SOA)

| Measurement/Event | Baseline | Day 1 | Day 2 | Day 3 | Day 4 | Day 5 | Day 7 | Day 14 | Day 28 | Day 60 | 3M | 6M | Post-discharge Call ^K |
|---|----------|----------------|----------------|----------------|----------------|----------------|----------------|----------------|----------------|--------|----|----|----------------------------------|
| Demographic/Admission Data/Medical Hx | X | | | | | | | | | | | | |
| Etiology of ARDS | X | | | | | | | | | | | | |
| Physical Exam | X | | | | | | | | | | | | |
| Height/Body weight | X | | | | | | | | | | | | |
| Time on ventilator prior to enrollment | X | | | | | | | | | | | | |
| Pregnancy test | X | | | | | | | | | | | | |
| Vital Signs (HR, SBP, DBP, MAP, T) ^B | X | X | X | X | X | X | X | | | | | | |
| Central venous pressure ^B | A | A | A | A | A | A | | | | | | | |
| Electrocardiogram (EKG) | X | X | X | X | A | A | X | | | | | | |
| Ventilator parameters ^{B, C} | X | X | X | X | X | X | X | X | | | | | |
| Chest X-ray (CXR) review ^D | X | A ^D | X | | | | | |
| Lung Injury Score (LIS) | X | X | X | X | X | X | X | X | | | | | |
| APACHE II Score | X | | | | | | | | | | | | |
| SOFA Score ^E | X | X | X | X | X | X | X | X | X ^F | | | | |
| Glasgow Coma Score (GCS) | X | X | X | X | X | X | X | X | X ^F | | | | |
| Richmond Agitation Sedation Scale (RASS) | X | X | X | X | X | X | X | X | | | | | |
| Arterial Blood Gas (ABG) | X | | | | | | | | | | | | |
| ABG; Venous Blood Gas if ABG not available ^C | | X | X | X | A | A | A | A | | | | | |
| Sp02 | X | X | X | X | X | X | X | X | A | | | | |
| ScvO ₂ | A | A | A | A | A | A | A | | | | | | |
| Complete blood count (CBC) ^C | X | X | X | X | A | A | A | A | A | | | | |
| Basic metabolic panel ^C | X | A | A | A | A | A | A | A | A | | | | |
| PT/PTT/INR ^C | A | A | A | A | A | A | A | A | | | | | |
| Serum CK, AST, ALT, Albumin, Total Protein ^C | A | A | A | A | A | A | A | A | | | | | |
| Total Bilirubin ^C | X | X | X | X | X | X | X | X | X | | | | |
| Lactate ^C | X | X | X | X | A | A | A | | | | | | |
| CO Administration Parameters / Treatment | | X ^G | X ^G | X ^G | | | | | | | | | |
| Pulmonary Dead Space (Vd/Vt) Measurement | | X | X | X | | | | X | | | | | |
| COHb and SpCO | | X ^G | X ^G | X ^G | | | | | | | | | |
| Vasopressors and inotropes ^B | X | X | X | X | X | X | X | X | X | | | | |
| Fluid intake and output ^B | X | X | X | X | X | X | | | | | | | |
| Renal replacement therapy status | X | X | X | X | X | X | X | X | X | | | | |
| Concomitant medications | X | X | X | X | X | X | X | | | | | | |
| Adverse event monitoring ^H | | X | X | X | X | X | X | X ^H | | | | | |

| Measurement/Event | Baseline | Day 1 | Day 2 | Day 3 | Day 4 | Day 5 | Day 7 | Day 14 | Day 28 | Day 60 | 3M | 6M | Post-discharge Call ^K |
|--|----------|-------|-------|-------|-------|-------|-------|--------|--------|--------|----|----|----------------------------------|
| Plasma isolation | | X | X | X | | | X | | | | | | |
| RNA banking | | X | X | X | | | X | | | | | | |
| DNA banking – Cell pellet isolation | | X | X | X | | | X | | | | | | |
| Primary cell (PBMC) isolation | | X | | | | | X | | | | | | |
| Urine sample collection | | X | X | X | | | X | | | | | | |
| Discarded BAL and plasma ^I | A | A | A | A | A | A | A | | | | | | |
| Microbiological results ^J | A | A | A | A | A | A | A | A | | | | | |
| Vital Status | | | | | | | | | | X | X | X | X |
| Discharge Status | | | | | | | | | | X | X | | X |
| Ventilator Status | | | | | | | | | | X | X | | X |
| Vasopressor Status | | | | | | | | | | X | X | | X |
| Neurocognitive Outcomes-MoCA-BLIND, Hayling | | | | | | | | | | | X | X | |

X - Required

A - When available

B - Data gathered at times indicated or until patient achieves 48 hours of unassisted breathing, whichever is sooner. Data will be obtained pre and post-treatment on study drug administration days.

C - Measure during reference period (03:00-10:00), obtain at time closest to study drug administration if applicable

D - CXRs done for clinical purposes will be reviewed on days 1-5. If the subject is extubated during days 1-5, a chest X-ray will be ordered by the study team the day following extubation, if not ordered by the clinical team.

E - Record clinically available creatinine, platelets, bilirubin, SBP and vasopressor use

F - Gathered on day 28 or on discharge date

G - Daily on days of study drug administration

H - AEs will be captured until study day 7

I - Obtained from discarded biobank (site specific) if available

J - Microbiological results recorded as they become available

K - If the subject is discharged home or to a long-term acute care facility before Day 28 or 60, he or she will be contacted by phone.

1.4 DEFINITIONS

Acute Kidney Injury: Acute kidney injury network Stage 3 disease, defined as a threefold increase in creatinine from baseline or the need for dialysis

Completing 48 hours of UAB (from weaning form): Defined as the date (calendar day) that the subject reaches exactly 48 hours of UAB. Example: if subject meets UAB at 1900 on 6/1/06 and does not return to AB, then the date of completing 48 hours of UAB would be 6/3/06.

Date of first UAB (from Study Termination form): Defined as the first day that the subject is on UAB from midnight to midnight. Example: if subject meets UAB at 1900 on 6/1/06, then the date of first UAB would be 6/2/06, as long as subject does not return to AB on 6/2/06.

Day zero: Defined as day of randomization. Study days are calendar days.

Drug held/hold drug: Study medication withheld for 24 hours.

Drug permanently discontinued: Study medication stopped for remainder of the trial.

Enrollment: All randomized participants will be included in the intent-to-treat (ITT) population. All randomized subjects who receive at least one dose of study product (CO vs. placebo) will be included in the safety analyses (*ie.* modified ITT). For secondary and exploratory endpoints, subjects may also be analyzed according to the number of study drug doses completed. Because some patients may withdraw or have a change in clinical status precluding dosing of study drug (eg. post-randomization lactic acidosis), we may randomize additional patients to achieve the enrollment goal of 36 patients who are randomized and treated with at least one dose of the study drug. We expect this to be an uncommon occurrence. Patients who are randomized but do not undergo any study procedures or study treatment will not be included in the study analysis.

Extubation: Removal of an orotracheal, nasotracheal tube, or unassisted breathing with a tracheostomy.

Home: level of residence or health care facility where the patient was residing prior to hospital admission

Hospital Mortality to Day 60: This primary endpoint includes all deaths following randomization in any health care facility prior to discharge “home” until study day 60. Study subjects still in a health care facility at study day 61 are considered alive for this endpoint.

Interruption of Dosing During Drug Administration: Study medication prematurely stopped prior to 90 minutes.

NYHA: New York Heart Association Class IV subjects (defined as subjects who have cardiac disease resulting in inability to carry out physical activity without discomfort. Symptoms of cardiac insufficiency or an anginal syndrome may be present even at rest. If any physical activity is undertaken, discomfort is increased).

Pneumonia: Unilateral or bilateral pulmonary infiltrates in a patient with suspected respiratory infection.

Sepsis: Life-threatening organ dysfunction caused by a dysregulated host response to infection:

1. Suspected or proven infection: Sites of infection include thorax, urinary tract, abdomen, skin, sinuses, central venous catheters, and central nervous system.
2. Increase in SOFA score greater than or equal to 2 over baseline.

Study Drug: Defined as inhaled carbon monoxide or placebo.

Study hospital: Defined as the hospital where the patient was enrolled.

Study withdrawal: Defined as permanent withdrawal from study before completion of study activities.

This does not include those subjects who have completed the protocol procedures or stopped procedures because they have reached unassisted breathing. If a patient or surrogate requests withdrawal from the study, the investigators will seek explicit permission to continue data collection.

UAB (Unassisted Breathing): Spontaneously breathing with face mask, nasal prong oxygen, or room air, T-tube breathing, tracheostomy mask breathing, or CPAP ≤ 5 without PS or IMV assistance, or the use of noninvasive ventilation solely for sleep-disordered breathing. Assisted breathing is any level of ventilator support at pressures higher than the unassisted breathing.

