6.1.4 CO MONITORING

The study drug concentration will be monitored continuously with the COventDS built-in analyzer to assure that the accurate dose is delivered. A physician investigator will assess subjects prior to daily iCO treatment. Subjects will have blood drawn daily for measurement of COHb and lactate prior to study drug administration. If COHb $\geq 3\%$ (assessed by unblinded physician) or lactate ≥ 4 mmol/L, the study drug will be held and the subject will be reassessed for treatment the following day. An electrocardiogram (EKG) will also be performed daily prior to study drug administration to evaluate for cardiac exclusion criteria. Blood COHb levels will be measured with an IL GEM Premier Co-oximeter and SpCO measured with a noninvasive pulse oximeter (Masimo Radical-7).

All CO monitoring will be carried out by the administering RT and physician study staff member OR physician study staff member alone and concealed from the study coordinator and clinical team. The physician study staff member will be responsible for maintaining a separate password-protected limited-access project within the database with the subject identification number and CO-related measurements (SpCO, COHb, ambient CO) which the study coordinator will not have access to.

Blood for COHb Monitoring

Blood (arterial or venous) will also be drawn at 20, 40, 60, 75, 90, and 180 minutes for safety monitoring of COHb levels. If an arterial line is not available, venous blood will be used for COHb monitoring as we³⁸ and others¹³⁷⁻¹³⁹ have shown that venous levels are as accurate and reliable as arterial measurements. Blood (arterial or venous) will also be drawn for blood gas analysis (using the IL GEM Premier Co-oximeter or local clinical lab) at 90 minutes or at the completion of treatment, if discontinued sooner than 90 minutes. If arterial blood is not available and venous blood gas is used, PaO_2/FiO_2 will be estimated using the formula $SpO_2/FiO_2 = 64 + 0.84 \times PaO_2/FiO_2$, as long as $SpO_2 \leq 97\%$ and subject remains intubated as described in the Statistical Analysis Plan.

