6.3 MEASURES TO MINIMIZE BIAS: RANDOMIZATION AND BLINDING

Eligible participants will be randomized to one of the two treatment arms using a permuted block method¹⁴⁶ with random block sizes. The randomization ratio will be 2:1 iCO:placebo. The randomization will not be stratified by any factors. The study biostatistician will verify all the necessary randomization information (blinding method, randomization method, block size, and number of treatment groups) in the StudyTRAX randomization configuration module.

Site investigators will review all potential study participants with one of the CCC physician members. Following informed consent, the unblinded administering RT or physician or blinded study coordinator will randomize subjects in the database using the StudyTRAX randomization tool. The unblinded administering RT or physician will obtain the subject's treatment assignment through the "View Treatment" button in the blinded database, a privilege granted to unblinded RTs and physicians only. CO-related measurements (SpCO, COHb, ambient CO) and drug-related information will be in a separate project within the database, which the blinded study coordinators will not have access to. Permission to this limited-access project will only be granted to unblinded study personnel by the PI, as it contains treatment-specific information such as CO monitoring and study drug administration data.

The study drug assignment will be blinded to the subject, clinical team, study coordinators, and other study staff with the exception of the administering study staff (RT and physician OR physician alone), who will be unblinded to the treatment assignment to ensure subject safety. We chose this partially double-blind design to ensure safe iCO administration and an unblinded assessment of COHb levels in order not to exceed potentially toxic thresholds.

To maintain blinding, the placebo air cylinders are identical in appearance as the CO cylinders (with the exception of different CGA valves required by the manufacturer Praxair). Cylinders will also be shrouded in dark sleeves to ensure blinding. The placebo air will be administered via inhalation via the COventDS

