7.2 PARTICIPANT DISCONTINUATION/WITHDRAWAL FROM THE STUDY

Participants are free to withdraw from participation in the study at any time upon request. An investigator may discontinue or withdraw a participant from the study for the following reasons:

- If any clinical AE, laboratory abnormality, or other medical condition or situation occurs such that continued participation in the study would not be in the best interest of the participant
- Disease progression which requires discontinuation of the study intervention
- If the participant meets an exclusion criterion (either newly developed or not previously recognized) that precludes further study participation
- Participant unable to receive at least one dose of the study drug

If a patient or surrogate requests withdrawal from the study, the investigators will seek explicit permission to continue data collection.

The reason for participant discontinuation or withdrawal from the study will be recorded on the Case Report Form (CRF). Subjects who sign the informed consent form and are randomized but do not receive the study intervention may be replaced. Subjects who sign the informed consent form, and are randomized and receive at least one dose of the study product, and subsequently withdraw, or are withdrawn or discontinued from the study will not be replaced.

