9.3 POPULATIONS FOR ANALYSES

All randomized participants will be included in the intent-to-treat (ITT) population. All randomized subjects who receive at least one dose of study product (CO vs. placebo) will be included in the safety analyses (*i.e.*.. modified ITT). For secondary and exploratory endpoints, subjects may also be analyzed according to the number of study drug doses completed.

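### Section 1.4 leaves some randomised patients out of the analysis although 1.4 and 9.3 define ITT as everyone randomised, and no population is named for mortality and free-day outcomes

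*Combined protocol and SAP*

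**What the plan says.** The Enrollment definition in 1.4 and section 9.3 open with the same rule: "All randomized participants will be included in the intent-to-treat (ITT) population". Both then set a narrower group for safety: "All randomized subjects who receive at least one dose of study product (CO vs. placebo) will be included in the safety analyses". Only 1.4 adds, as its last sentence: "Patients who are randomized but do not undergo any study procedures or study treatment will not be included in the study analysis".

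On replacement, 1.4 says "we may randomize additional patients to achieve the enrollment goal of 36 patients who are randomized and treated with at least one dose". It names withdrawal or a change in clinical state as the cause, gives lactic acidosis after randomisation as its example, and expects this to be uncommon. Section 7.2 agrees: "Subjects who sign the informed consent form and are randomized but do not receive the study intervention may be replaced". It also lists, among the reasons an investigator may withdraw someone, "Participant unable to receive at least one dose of the study drug".

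Four other provisions matter:
- Section 8.3.1 allows up to 24 hours between randomisation and first dose.
- Section 6.3 exempts the administering staff from blinding, "who will be unblinded to the treatment assignment to ensure subject safety".
- Section 8.7.5 does not collect adverse events before the first dose unless a protocol procedure may have caused them.
- Section 5.4 puts patients extubated before finishing the three treatment days on a modified ITT basis.

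**The concern.** Two rules for the same patients give different answers, and the section that should govern (9.3) repeats only one of them. An analyst would have to choose, possibly with the data in view.

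The choice matters for outcomes compared between arms. A patient who is randomised and never dosed may have deteriorated, withdrawn or come off the ventilator, and such reasons are tied to prognosis. If these patients leave the analysis of mortality or free days, the groups compared are no longer those formed by randomisation. At least one person at the bedside may know the allocation when the first dose is or is not given. Because adverse events before dosing are mostly not collected, the final data might show little about who was lost or why.

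**Working it through.** **1. Who is in the analysis.** Setting the rules side by side gives three classes of randomised patient.

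| Class | ITT rule (1.4, 9.3) | Last sentence of 1.4 | Safety set | May be replaced |
|---|---|---|---|---|
| Dosed at least once | in | in | in | no |
| Undosed, had some study procedure | in | not excluded | out | yes |
| Undosed, no study procedure | in | **out** | out | yes |

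The direct contradiction is in the third row. Its border with the second is unclear, because the plan does not define a study procedure. Whether a baseline assessment (8.4) or a pre-dose COHb draw, EKG or dead-space measurement (8.5.2) counts could decide whether a patient is analysed.

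**2. The mortality definition.** Section 1.4 counts in-facility deaths from randomisation to Day 60. A third-row patient who dies is an event under that definition and absent under the Enrollment definition. (That entry calls mortality a primary endpoint; 1.1, 3 and 9.1 list it as secondary, which I take as intended.)

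**3. Population by endpoint.** Section 9.3 assigns only safety. It allows secondary endpoints to be analysed additionally by number of doses completed. Section 9.4.3 plans a Cox hazard ratio for death and ANCOVA for the free-day outcomes without naming a population. Section 5.4 points towards modified ITT for some patients.

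**4. Who decides on a first dose.** Sections 6.3 and 8.3.1 let the administering RT or physician view the assignment after randomisation. No section requires the decision not to give a first dose, or a withdrawal under 7.2, to be made by someone blinded.

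**5. The plan's own loss figure.** Section 9.2 allows 8% dropout. Table 6 is labelled n = 24 and n = 12, and the formula is 1 − (1 − p)^n.
- CO, p = 0.10: n = 24 gives 0.920; n = 22 (24 × 0.92 = 22.1) gives 0.902. The table has 0.90.
- Placebo, p = 0.15: n = 12 gives 0.858; n = 11 (12 × 0.92 = 11.0) gives 0.833. The table has 0.83.

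All 14 cells match at 22 and 11. So the plan budgets for 8% loss and also replaces undosed patients. The 8% is not a forecast of non-dosing; I use it as one point in a range.

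**6. How many could be undosed.** To reach 36 treated with an undosed share u, the number randomised is 36/(1 − u), rounded up. The values of u are assumptions.

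| u | Randomised | Undosed |
|---|---|---|
| 3% | 38 | 2 |
| 5% | 38 | 2 |
| 8% | 40 | 4 |
| 10% | 40 | 4 |
| 15% | 43 | 7 |

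Only those with no study procedure fall under the exclusion in 1.4. All of them are lost if the analyst uses the dosed set instead.

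**7. Weight of one patient.** Placebo: 1/12 = 8.3% of the arm. iCO: 1/24 = 4.2%.

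**8. Illustration, with assumed deaths.** The arms are kept at 24 and 12 dosed, since replacement refills the total, and every omitted patient is assumed to have died.
- iCO: 7/24 = 29.2% among dosed becomes 8/25 = 32.0%, 9/26 = 34.6% or 10/27 = 37.0% when 1, 2 or 3 are restored, a shift of about 3 to 8 points.
- Placebo at an assumed 30% risk (3.6/12): 4.6/13 = 35.4% or 5.6/14 = 40.0% when 1 or 2 are restored, a shift of about 5 to 10 points.

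**The case against.** The strongest reply is that the exclusion is narrow and unlikely to bite. It requires neither procedures nor treatment, and a consented patient usually has baseline assessments and pre-dose checks. Non-dosing is expected to be uncommon, patients not expected to survive 24 hours are excluded at entry (5.2), and section 9.3 does not repeat the exclusion. Allowing secondary endpoints to be analysed additionally by doses completed also suggests that ITT is the main set for them. This is a Phase Ib trial whose primary endpoints are safety and COHb accuracy, and 9.4.3 concedes power only for large changes.

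Much of this stands, and it rules out several stronger inferences.
- A reader might infer that every untreated patient is dropped. The sentence does not say so; the second row of the table stays in ITT.
- A reader might infer that replacement removes the patient replaced. Neither 1.4 nor 7.2 says that; they only permit further randomisation.
- A reader might infer that a Day 1 hold takes a patient out. Under 6.1.6 a COHb or lactate hold lasts until the next scheduled dose, when both are measured again, so a later dose can follow. The thresholds are numeric and the same in both arms.
- A reader might infer that every hold is decided with the allocation known. In 6.1.4 the phrase "assessed by unblinded physician" attaches to COHb only, and a COHb level before the first dose cannot depend on the arm.
- A reader might picture the placebo arm shrinking by the number excluded. That ignores replacement, and any such mortality figures would be invented.

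What the reply does not remove is the contradiction itself, the undefined term on which it turns, and the missing population for the clinical outcomes.

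**Conclusion.** The concern holds in a limited form. Section 1.4 contradicts itself, section 9.3 and its own Day 60 mortality definition. The plan also names no population for mortality or ventilator-, ICU- and hospital-free days, so those analyses cannot be run without an unrecorded choice.

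Bias in these comparisons is possible, not demonstrated. Its direction is unknown: omitting deaths flatters whichever arm loses them, and a patient extubated before a first dose would be lost with a good outcome. The firm figure is the weight of one patient, 8.3% of the placebo arm or 4.2% of the iCO arm. The shifts of roughly 3 to 10 points above rest on assumed event counts and on every omitted patient having died.

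The documents do not show that arms have been or will be thinned by someone who knows the allocation. They show only that no rule prevents it. The dosed set is the right one for the primary safety and COHb analyses. The text is wrong as written; severity is moderate and confined to secondary endpoints.

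**What to change.** - **1.4:** delete the last sentence of the Enrollment definition.
- **9.3:** state that mortality and ventilator-, ICU- and hospital-free days are analysed in all randomised patients, including any who were replaced, and that safety and COHb accuracy use the dosed (modified ITT) set. Bring the modified ITT remark in 5.4 into line.
- **7.2:** state that undosed or replaced patients stay in follow-up for vital and ventilator status unless permission is refused.
- **Reporting:** list undosed patients by arm with the reason, recorded where possible by someone blinded to allocation.

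The cost is small. Vital, discharge and ventilator status at Days 28 and 60 are already scheduled (8.1), and death-index matching is planned (7.3). There would be a few more patients to follow: 2 to 7 under the assumed range, 4 at 8%. Some data will be missing, because after a withdrawal requested by the patient or surrogate, data collection continues only with explicit permission (1.4, 7.2). Those gaps should be counted by arm.
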